#### 3.2.2 Secondary Outcome Measures

- Cumulative incidence of Grade 3 or higher unsolicited adverse events, safety laboratory adverse events, or serious adverse events
- Cumulative incidence of absolute neutrophil counts below 500/mm^3
- Cumulative incidence of transaminase elevation during treatment  $\geq 2$ -times the baseline value
- Cumulative incidence of adverse events leading to permanent discontinuation of valganciclovir therapy, or any adverse event that is not recovered / not resolved

- 
- Cumulative incidence of sensorineural hearing loss in at least one ear between Baseline and Study Month 4 [both ears with normal hearing at baseline, then at least one ear with sensorineural hearing loss (SNHL) at the 4 month follow-up]
  - Cumulative incidence of sensorineural hearing loss in at least one ear between Baseline and Study Month 12 [both ears with normal hearing at baseline, then at least one ear with sensorineural hearing loss (SNHL) at the 12 month follow-up]
  - Cumulative incidence of sensorineural hearing loss in at least one ear between Baseline and Study Month 18 [both ears with normal hearing at baseline, then at least one ear with sensorineural hearing loss (SNHL) at the 18 month follow-up]
  - Cumulative incidence of each degree of worsened hearing (mild, moderate, severe, profound) at Study Months 4, 6, 12, and 18, represented by the ear that has the larger degree of worsening
  - Proportion of ears of each degree of worsened hearing (mild, moderate, severe, profound) at Study Months 4, 6, 12, and 18

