### **6.3.1 Neutropenia**

If the ANC reproducibly (within one week) decreases to  $< 500$  cells/mm^3, valganciclovir will be held until the ANC recovers to  $\geq 750$  cells/mm^3, and then administration of drug will resume at the normal dose. If the ANC again reproducibly (within one week) decreases to  $< 750$  cells/mm^3, the valganciclovir dosage will be reduced by 50% and maintained there as long as the ANC remains  $\geq 500$  cells/mm^3. If the ANC reproducibly (within one week) decreases to  $< 500$

---

cells/mm^3 on the 50% dosage, then the study medication will be discontinued. Administration of granulocyte colony stimulating factor (GCSF) is allowed. All administered GCSF doses will be recorded on the concomitant medication sheet. The decision to utilize GCSF is left to the medical discretion of the participating investigator. The parameters for dose adjustment stated above, based upon ANC, will remain in effect even if the patient is receiving GCSF.

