### **9.5.2 Discontinuation of Study Enrollment, and Study Treatment For All Subjects, Pending Sponsor Review**

Enrollment and study product administration will be halted for Safety Monitoring Committee (SMC) review/recommendation if any of the following is reported:

- Two or more subjects experience a study product-related SAE.
- 10% or more subjects (with a minimum of 3 subjects) experience the same severe (Grade 3 or higher) study product-related unsolicited AE.
- 20% or more subjects (with a minimum of 3 subjects) experience the same severe (Grade 3 or higher) study product-related non-neutropenia safety laboratory AE.
- 30% or more subjects (with a minimum of 3 subjects) experience severe (Grade 3 or higher) study product-related neutropenia safety laboratory AE.
- 10% or more subjects (with a minimum of 3 subjects) permanently discontinue study treatment according to the criteria outlined in Section 6.3.

Additionally, DMID and the Central Unit may interrupt study dosing and/or study entry at any time if medically indicated. To minimize risk, the medical monitor and the SMC will review cumulative safety data. If enrollment is halted based upon the study halting criteria above or the review of the safety data, upon completion of the review and receipt of advice of the SMC, DMID and the Central Unit Administration will determine if study entry or study dosing may continue according to the protocol.

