### **11.4.3 Safety Analysis Plan**

Safety evaluations will be based on the incidence, severity, and type of AEs. Safety variables will be tabulated and presented for all subjects in the safety population. All tests will use a 5% significance level, i.e.,  $p$ -values  $< 0.05$  will be considered significant, and for estimation a 95% confidence level will be used.

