### **11.4.4 Efficacy Analysis Plan**

Primary analysis:

The primary analysis is estimating the proportion of subjects with asymptomatic congenital CMV infection who, following treatment with 4 months of oral valganciclovir, develop SNHL by 6 months of life in at least one ear. Due to the small expected number of subjects who will develop SNHL by 6 months, the Clopper-Pearson method will be used to calculate an exact 95% upper confidence bound for the primary outcome.

Secondary analyses:

---

For the proportion of subjects who develop SNHL at 4, 12, and 18 months post baseline, we will also use the Clopper-Pearson method to obtain an estimate of the 95% upper confidence bounds separately for each period. In each of these hearing outcomes, we will provide a breakdown on the degree of worsening (mild, moderate, severe). This method will also be used to define safety and tolerability of valganciclovir by estimating the incidence of adverse events of interest. If there is enough information in the data collected, we will use a large-sample method for estimating the 95% confidence interval of interest over the more conservative Clopper-Pearson method.

Analysis of actual viral load will be done using log base 10 transformation for both whole blood and plasma CMV viral loads. Undetectable viral load value will be replaced by a value of 10. To investigate the change over time, we will model the log base 10 viral load using mixed model to accommodate repeated measures. The covariance structure (selected among unstructured, exchangeable, autoregressive, exponential, and toeplitz) that best describes the correlation among the repeated measures over time will be selected using the AIC model selection index. Note that there will be 13 time points for which viral load will be measured. Hence, if time will be represented as discrete variables in the model, this will require spending 12 degrees of freedom in the model, which we believe is unnecessary. In our modeling we will represent time as a continuous variable and will consider fitting linear, quadratic, and cubic to approximate non-linear trends. The simplest model with a good fit based on the test of the coefficients, as well as the profile curves, will be selected. Modeling will be done separately for whole blood and plasma viral loads.

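### GCSF is given at discretion and left out of the safety analysis, so the ANC-below-500 count and the neutropenia discontinuation count can understate drug toxicity

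*Combined protocol and SAP*

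**What the plan says.** On GCSF, section 6.3.1 has four sentences that matter here. One permits it: "Administration of granulocyte colony stimulating factor (GCSF) is allowed". Another leaves its use to judgement at each site: "The decision to utilize GCSF is left to the medical discretion of the participating investigator". A third concerns data capture: "All administered GCSF doses will be recorded on the concomitant medication sheet". The last deals with study-drug dosing while an infant is on GCSF: "The parameters for dose adjustment stated above, based upon ANC, will remain in effect even if the patient is receiving GCSF". No neutrophil count or other trigger for GCSF is stated, and the dose rules run on the measured count whether or not GCSF is supporting it.

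The endpoint in 3.2.2 is "Cumulative incidence of absolute neutrophil counts below 500/mm" (per cubic millimetre), a laboratory value and nothing else.

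On analysis, 11.4.3 says: "Safety evaluations will be based on the incidence, severity, and type of AEs". After naming the Clopper-Pearson method, 11.4.4 adds: "This method will also be used to define safety and tolerability of valganciclovir by estimating the incidence of adverse events of interest". Neither section treats GCSF as an event, an intercurrent event, a sensitivity analysis or a planned table. Section 11.4.5, on missing values and outliers, does not mention it either.

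Two halting rules in 9.5.2 depend on the same counts. One is met when at least 10% of subjects (minimum 3) "permanently discontinue study treatment according to the criteria outlined in Section 6.3". The other is met when at least 30% (minimum 3) have product-related neutropenia of Grade 3 or higher. Section 9.6 lets reports to the Safety Monitoring Committee (SMC) include concomitant medications but does not require GCSF to be shown with neutropenia.

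**The concern.** Sections 2.2 and 2.3.1 name neutropenia as the main toxicity of valganciclovir. The infants are asymptomatic, so a reader weighing benefit against risk will rely on the neutropenia figures. GCSF raises the count on which those figures rest. If it starts before an infant has had a count below 500 and the count then stays at or above 500, the infant is scored as free of that event although the marrow needed support. The error runs one way: early GCSF can remove events from the count but cannot add any.

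Two features of the trial make this harder to see. There is no control arm, and use is left to judgement across 9 sites. Section 2.2 also argues from neutropenia rates compared across studies (19% against 21%). If a similar comparison is later made with this trial's rates, unreported GCSF use would weaken it.

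**Working it through.** **1. Which counts can be affected, and when.**

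- *ANC below 500 (3.2.2).* This is a cumulative incidence, so one recorded count below 500 is an event whatever follows. The requirement in 6.3.1 that a fall be reproducible governs dosing, not the endpoint. Only GCSF started before the first such count can matter.
- *Discontinuation for neutropenia (6.3.1, feeding 9.5.2).* The path runs through a reproducible fall below 500, a later one below 750, and another below 500 on half dose. GCSF given after the first fall can prevent the later ones, so this count does not depend on early use. Discontinuations for platelets or ALT, which enter the same 10% rule, are not affected by this argument.
- *Grade 3 or higher laboratory endpoint and the 30% rule.* After 7 days of age, Appendix A grades 400 to 599 as Grade 3 and below 400 as Grade 4. These counts are affected only if GCSF starts before a Grade 3 value, that is at 600 or above.

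**2. The planned method.** The plan states no expected rate or precision for the neutropenia endpoint, so there is no figure of its own to reproduce. The method can be checked on Table 3. With x events in n infants, the one-sided 95% Clopper-Pearson upper bound is the 0.95 quantile of Beta(x+1, n−x). For n = 176 and x = 0, 1, 2 it gives 1.69%, 2.67% and 3.53%. Table 3 has 1.69%, 2.67% and 3.50%; the 0.03-point difference in the last cell has no bearing here.

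**3. Illustration.** From 11.2, N = 229 − 11 = 218 expected to enrol, all taken as dosed. Two quantities are assumptions, not document figures: p, the risk of ANC below 500 without GCSF, and g, the share of would-be events averted by early GCSF. Counted events = N × p × (1 − g), rounded. For example, 218 × 0.10 × 0.75 = 16.35, so 16. Each cell gives events, estimate and upper bound.

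| p | g = 0 | g = 10% | g = 25% | g = 50% |
|---|---|---|---|---|
| 3% | 7; 3.2%; 5.9% | 6; 2.8%; 5.4% | 5; 2.3%; 4.8% | 3; 1.4%; 3.5% |
| 10% | 22; 10.1%; 14.1% | 20; 9.2%; 13.1% | 16; 7.3%; 10.9% | 11; 5.0%; 8.2% |
| 20% | 44; 20.2%; 25.2% | 39; 17.9%; 22.7% | 33; 15.1%; 19.7% | 22; 10.1%; 14.1% |

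Apart from rounding, the estimate falls in proportion to g. The upper bound drops below the assumed risk at p = 10% with g = 50%, and at p = 20% with g = 25% or 50%. At g = 10% the estimate moves by 0.9 points or less for p = 3% or 10% (22/218 − 20/218 = 0.9) and by 2.3 points for p = 20%.

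**4. Where p might lie.** The nearest document figures are in 2.1, from the earlier randomised trial in symptomatic infants. Three participants had drug suspended for ANC below 500 (3/109 = 2.8%, if 109 is the denominator), and 21 of 109 (19.3%) had Grade 3 or 4 neutropenia in the first six weeks. Neither is a direct estimate of p. The first makes the 3% row plausible; the second is a different class of event.

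**The case against.** The strongest reply is that observed ANC under the regimen as delivered, with GCSF permitted, is a legitimate treatment-policy measure of safety, and the protocol never claims to estimate risk without GCSF. That stands, and it is why the endpoint should not be replaced. It does not explain why the plan is silent on GCSF: a treatment-policy figure still needs the amount of rescue shown beside it.

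A reader might go further and infer that an infant given GCSF at a count of 550 who never falls below 500 leaves no trace in the safety results. The documents do not support this. After 7 days of age, 550 is Grade 3 in Appendix A, so the infant counts in the Grade 3 or higher laboratory endpoint. Section 9.3.3 presumes on-treatment neutropenia to be associated with study drug, so the infant should also count toward the 30% rule. At that age, counts of 600 to 1,000 are Grade 1 or 2, and such laboratory AEs are documented under 9.2.1, subject to the baseline exception in 9.2.3. What such an infant can escape is the ANC-below-500 endpoint.

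A reader might also infer that GCSF does hide toxicity in this trial, or by how much. The documents give no rate of GCSF use, so only the possibility is established. The 10% and 20% rows and every value of g are assumptions.

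Finally, counting GCSF as an event may include infants who would never have fallen below 500. That is a fair objection to using the composite as the endpoint, but not to using it as a labelled supportive analysis. Rates by site would be imprecise, at about 218/9 = 24 infants each.

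**Conclusion.** The point holds in a limited form. Discretionary GCSF with no stated trigger, an endpoint on observed ANC below 500 alone, and an analysis plan that does not mention GCSF together mean that two counts can be understated as measures of drug toxicity: the ANC-below-500 incidence, through early GCSF, and neutropenia discontinuations under Section 6.3, through GCSF after a first fall. The Grade 3 or higher endpoint is exposed only where GCSF starts before a Grade 3 count.

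The size cannot be found from the documents. Under the assumptions shown, averting a quarter to a half of events lowers the estimate by about 1 to 2 points at a 3% risk and about 3 to 5 points at a 10% risk. If early GCSF is rare, the effect is small. No number can be put on the discontinuation effect. The primary hearing-loss analysis is not touched. The gap lies mainly in the analysis plan, since every GCSF dose is already to be recorded. It is worth closing because it concerns the drug's main toxicity, runs in one direction and has no control arm to reveal it.

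**What to change.** Keep observed ANC below 500 as the endpoint in 3.2.2, and make three additions.

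- **Supportive analysis (11.4.3 and 11.4.4).** Prespecify a second incidence that counts an infant as an event if there is any ANC below 500 or if GCSF was given for neutropenia, with the same Clopper-Pearson method. Label it an upper-side estimate, because it may include infants who would not have fallen below 500. If all infants whose events GCSF averted are captured, the observed endpoint and this one bracket the rate without GCSF.
- **Table.** Show the number of infants given GCSF, its timing, and the last ANC before the first dose, beside the neutropenia and discontinuation counts. Put it in the final report and in SMC reports, so that the 10% and 30% rules are read with GCSF use in view.
- **Indication.** Record the reason for GCSF with each dose. Sections 6.3.1 and 6.6.1 require the drug to be recorded but do not say that its indication is captured.

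The cost is a few sentences in the analysis plan, one table and one data field if the indication is not already collected. The supportive rate may look less favourable than the observed one. Nothing here changes or proposes a rule on when GCSF is given or how study drug is dosed.

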### **6.3.2 Thrombocytopenia**

If the platelet count at baseline was  $\geq 100,000/\text{mm}^3$ , then valganciclovir may be held if the platelet count reproducibly (within one week) decreases to  $< 50,000/\text{mm}^3$ . After the platelet count increases to  $\geq 50,000/\text{mm}^3$ , valganciclovir administration at the normal dose may resume. If the platelet count at baseline was  $< 100,000/\text{mm}^3$ , then valganciclovir may be held if the platelet count reproducibly (within one week) decreases by 50% from baseline value. After the platelet count increases above 50% from baseline value, valganciclovir administration at the normal dose may resume. Recurrence of platelet count below these thresholds will lead to study drug discontinuation.

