#### 5.3.3.2 Reasons for Withdrawal During Treatment

The criteria for discontinuations during the time that study medication is being provided include:

- Discontinuation of Study Product
  - Development of a related serious adverse event warranting withdrawal of therapy
  - Deterioration in general condition for which alternative treatment is indicated and which, in the opinion of the investigator, warrants withdrawal of therapy
  - Development of a medical disease or condition, or any new clinical findings for which continued participation, in the opinion of the site principal investigator or appropriate sub-investigator, would compromise the safety of the subject, would interfere with the subject's successful completion of this study, or would interfere with the evaluation of responses.
- Subject Withdrawal
  - Study subject (parent/legal guardian) wishes to withdraw
  - Non-compliance with study procedures or medication schedule that in the opinion of the investigator warrants withdrawal
  - The study is terminated
  - Any other reason which, in the opinion of the investigator, precludes the study subject's participation in the study. The site principal investigator must call the study Principal Investigator (or designee) prior to discontinuing a study subject for this reason.

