## **6.3 Modification or Termination of Study Intervention/Investigational Product for a Participant**

Bone marrow suppression secondary to CMV can mimic valganciclovir toxicity. Nevertheless, the dosage of valganciclovir will be reduced or terminated if any of the following occur:

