### **6.3.3 Hepatotoxicity**

If the ALT reproducibly (within one week) increases to  $\geq 5$ -times the baseline value, valganciclovir will be held until ALT falls to  $\leq 2$ -times the baseline value, at which time valganciclovir will be restarted. If the ALT again increases  $\geq 5$ -times the baseline value, study drug will be discontinued.

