## **9.5 Halting Rules**

### **9.5.1 Discontinuation of Study Participation for Individual Subject**

Subjects with neutropenia, thrombocytopenia, or hepatotoxicity while on study medication will be discontinued from study treatment if the criteria outlined in Section 6.3 (Modification or

---

Termination of Study Intervention/Investigational Product for a Participant) or in Section 5.3.3 (Reasons for Withdrawal) are met. Since the primary endpoint requires comparison of baseline and 6 month audiology assessments, dropouts and subjects with audiology assessments that are inadequate for study comparison will be replaced in order to reach the target of sample size.

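### The hold for a confirmed platelet fall in 6.3.2 is optional, so no specific mandatory action is defined for a Grade 3-4 count that does not recover, in conflict with the 6.3 lead-in and the ANC and ALT rules

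*Combined protocol and SAP*

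**What the plan says.** Section 6.3.2 has two strata by baseline platelet count.

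- Baseline at least 100,000/mm³: "then valganciclovir may be held if the platelet count reproducibly (within one week) decreases to" below 50,000/mm³.
- Baseline below 100,000/mm³: "then valganciclovir may be held if the platelet count reproducibly (within one week) decreases by 50% from baseline value".

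After recovery, dosing at the normal dose *may* resume in either stratum. The one compulsory sentence is the last: "Recurrence of platelet count below these thresholds will lead to study drug discontinuation".

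The neighbouring rules are worded differently. In 6.3.1, after a confirmed neutrophil count below 500 cells/mm³, "valganciclovir will be held until the ANC recovers to" at least 750. In 6.3.3, after a confirmed ALT of at least 5 times baseline, "valganciclovir will be held until ALT falls to" no more than 2 times baseline. The lead-in to all three subsections says that "the dosage of valganciclovir will be reduced or terminated if any of the following occur".

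**The concern.** A rule that compels action only on recurrence does not reach a count that never recovers. An infant whose platelets rebound and fall again must come off drug. An infant whose confirmed low count simply persists may, under 6.3.2, stay on full dose. The worse course has the weaker rule, and the neutrophil and ALT rules do not share this feature.

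At stake is the protection of the individual infant and consistent dosing across the 9 sites. Section 2.3.1 lists thrombocytopenia among the drug's hematologic toxicities, and 2.3.2 accepts that these asymptomatic infants may gain no direct benefit. A defined hold suits that balance.

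**Working it through.** There is no plan figure to reproduce. The check is a comparison of the rules, a grading of the triggers, and simple dose arithmetic for the cost of a hold.

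**1. The rules side by side**

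| Rule | Confirmed trigger | While abnormal | After recovery | Next event |
|---|---|---|---|---|
| 6.3.1 ANC | < 500 | *will* be held | resumes at normal dose | < 750: dose halved; < 500 on half dose: stop |
| 6.3.3 ALT | ≥ 5 × baseline | *will* be held | restarted | ≥ 5 × baseline again: stop |
| 6.3.2 platelets, baseline ≥ 100,000 | < 50,000 | *may* be held | *may* resume | recurrence: stop |
| 6.3.2 platelets, baseline < 100,000 | 50% fall | *may* be held | *may* resume | recurrence: stop |

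Only the platelet rows lack a compulsory step while the abnormality lasts.

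**2. Severity of the triggers (Appendix A)**

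Grade 3 is 25,000 to below 50,000; Grade 4 is below 25,000.

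- First stratum: the trigger is below 50,000, so Grade 3 or 4.
- Second stratum: the trigger is 0.5 × baseline with baseline below 100,000, so it is always below 50,000. Examples: 0.5 × 90,000 = 45,000 (Grade 3); 0.5 × 60,000 = 30,000 (Grade 3); 0.5 × 48,000 = 24,000 (Grade 4).

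**3. Whether another provision requires a hold for the individual infant**

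- The 6.3 lead-in says action will follow but names only reduction and termination. Section 6.3.2 has no reduction step, and its only termination step is recurrence. The first step for ANC and ALT is a hold, which the lead-in does not name either. It conflicts with 6.3.2 without telling a site what to do.
- Section 9.5.1 compels discontinuation if the 6.3 criteria, "or in Section 5.3.3 (Reasons for Withdrawal) are met". The first route returns to recurrence. On the second, the closest criterion in 5.3.3.2 is a condition for which continuing, "in the opinion of the site principal investigator or appropriate sub-investigator, would compromise the safety of the subject", so it rests on judgment.
- Section 9.3.3 requires notice to the data coordinating center within 24 hours of any count below 50,000. That is reporting, not dosing.
- Section 9.5.2 acts on the cohort: at least 2 infants with a related SAE, or at least 3 infants (and 20%) with the same related Grade 3 or higher laboratory event. The sponsor and the Central Unit *may* interrupt dosing at any time.

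None of these defines a compulsory hold for a first affected infant.

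**4. Dose arithmetic**

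Dosing is twice daily (6.2.1). One week held = 7 × 2 = 14 doses. Taking four months as 120 days, the course is 120 × 2 = 240 doses, and 14/240 = 5.8%. With 112 days it is 14/224 = 6.3%; with 122 days, 14/244 = 5.7%.

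Longer gaps between visits do not translate directly into doses given at a low count, because 6.3.2 needs the fall to be reproduced within one week. After Day 42 scheduled counts are 14 days apart. Even with the visit windows, the shortest gap from Day 42 to Day 56 is (56 − 3) − (42 + 3) = 8 days, and the same holds through Day 84. From Day 84 to Month 4 the gap is longer still. On scheduled counts alone, no new fall after Day 42 can be confirmed in time. Gap figures of 28 doses (14 × 2) or 72 doses ((120 − 84) × 2) therefore apply, without extra testing, only to a count already confirmed low by Day 42.

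**The case against.** A reader might infer that a persistent Grade 3-4 count triggers no required dosing action at all. The documents do not support that. Read literally, the 6.3 lead-in requires action whenever a listed event occurs. The supportable statement is that the lead-in and 6.3.2 conflict and that no specific compulsory step is defined.

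The stronger defence is that the discretion was intended. Section 6.3.2 uses *may* for both holds and both resumptions, then *will* for recurrence, which looks deliberate. The lead-in acknowledges that CMV marrow suppression can mimic drug toxicity, so continuing through a low count might be reasonable. But the same sentence goes on to say that action will nevertheless follow. The intent is therefore unclear, and the plan gives no reason for treating platelets differently from neutrophils or ALT. Even if discretion was intended, the rule is stricter for the infant who recovers and relapses than for the one who never recovers.

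The practical reach is small, and that part of the objection stands. Section 5.2 excludes thrombocytopenia, if known, and baseline platelets are drawn between Day -3 and Day 1, so the second stratum should be nearly empty. A count below 50,000 would be noticed through the 24-hour report, and most investigators would probably hold drug anyway. A reader might also infer that many infants would be dosed at low counts, or that the hearing results would be affected; nothing in the documents supports either.

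**Conclusion.** The point holds as an inconsistency in the dosing rules. The hold in 6.3.2 is optional in both strata, a stop is compelled only on recurrence, and no specific mandatory action is defined for a confirmed Grade 3-4 platelet count that does not recover. This conflicts with the 6.3 lead-in and with the compulsory holds in 6.3.1 and 6.3.3.

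It is a minor safety-wording matter worth correcting. The number of infants affected is not given and is likely to be small. The conclusion rests on the text and on the Appendix A grades. The dose percentages alone depend on the assumed length of four months.

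**What to change.** 1. In 6.3.2, change the hold from *may* to *will* in both strata, at least until the platelet count is ≥ 50,000/mm³ (baseline ≥ 100,000) or above 50% of the baseline value (baseline < 100,000). The second recovery point is read here as half of baseline.
2. Keep *may* for resumption. In the second stratum the recovery point lies below 50,000, so automatic resumption could direct full dosing at a count just above 45,000, 30,000 or 24,000 in the examples above, which can still be Grade 3 or 4. The investigator should remain free to wait.
3. Leave the thresholds and the recurrence rule unchanged.
4. In the 6.3 lead-in, let the actions that will follow read *held, reduced or discontinued*.

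These are wording edits with no new tests. Sites lose the discretion to continue drug through a confirmed low count, so a few infants may miss doses at 14 per week held. An infant held to the end would not complete four months of drug and so would fall outside the per protocol population in 11.4.1.2, as can already happen under the ANC and ALT holds. A time limit for non-recovery could be added but is not essential, since a compulsory hold already keeps drug off.
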